APPENDIX 2. PARTIAL DATE CONVENTIONS

Imputed dates will NOT be presented in the listings.

Algorithm for Treatment Emergence of Adverse Events:

START DATE	STOP DATE	ACTION
Known	Known/Partial/ Missing	If start date < study med start date, then not TEAE If start date >= study med start date, then TEAE
Partial, but known components show that it cannot be on or after study med start date	Known/Partial/ Missing	Not TEAE
Partial, could be on or after study med start date OR Missing	Known	If stop date < study med start date, then not TEAE If stop date >= study med start date, then TEAE
	Partial	Impute stop date as latest possible date (i.e. last day of month if day unknown or 31st December if day and month are unknown), then: If stop date < study med start date, then not TEAE If stop date >= study med start date, then TEAE
	Missing	Assumed TEAE

Document: \\weedc-vnasc01\Biosdata\Menarini\NebAm\ZZA67778\Biostatistics\Documentation\SAP\SAP_Menarini_MEIN21AmNe-Hyp001_Final_V1.0

Author: [name]

Version Number:

Final V1.0

Version Date:

11Nov2022

Template No.: CS_TP_BS016 Revision 7

Reference: CS_WI_BS005

Effective Date: 01Nov2021

Algorithm for Prior / Concomitant Medications:

START DATE	STOP DATE	ACTION
Known	Known	
If stop date < study med start date, assign as prior
 
If stop date >= study med start date and start date <= study med end date, assign as concomitant
 
If stop date >= study med start date and start date > study med end date, assign as post study

	Partial	
Impute stop date as latest possible date (i.e. last day of month if day unknown or 31st December if day and month are unknown), then:
 
If stop date < study med start date, assign as prior
 
If stop date >= study med start date and start date <= study med end date, assign as concomitant
 
If stop date >= study med start date and start date > study med end date, assign as post treatment

	Missing	
If stop date is missing could never be assumed a prior medication
 
If start date <= study med end date, assign as concomitant
 
If start date > study med end date, assign as post treatment

Partial	Known	
Impute start date as earliest possible date (i.e. first day of month if day unknown or 1st January if day and month are unknown), then:
 
If stop date < study med start date, assign as prior
 
If stop date >= study med start date and start date <= study med end date, assign as concomitant
 
If stop date >= study med start date and start date > study med end date, assign as post treatment

Document: \\eedc-vnasc01\Biosdata\Menarini\NebAm\ZZA67778\Biostatistics\Documentation\SAP\SAP_Menarini_MEIN21AmNe-Hyp001_Final_V1.0

Author: [name]

Version Number:

Final V1.0

Version Date:

11Nov2022

Template No.: CS_TP_BS016 Revision 7

Reference: CS_WI_BS005

Effective Date: 01Nov2021

START DATE	STOP DATE	ACTION
	Partial	
Impute start date as earliest possible date (i.e. first day of month if day unknown or 1st January if day and month are unknown) and impute stop date as latest possible date (i.e. last day of month if day unknown or 31st December if day and month are unknown), then:
 
If stop date < study med start date, assign as prior
 
If stop date >= study med start date and start date <= study med end date, assign as concomitant
 
If stop date >= study med start date and start date > study med end date, assign as post treatment

	Missing	
Impute start date as earliest possible date (i.e. first day of month if day unknown or 1st January if day and month are unknown), then:
 
If stop date is missing could never be assumed a prior medication
 
If start date <= study med end date, assign as concomitant
 
If start date > study med end date, assign as post treatment

Missing	Known	
If stop date < study med start date, assign as prior
 
If stop date >= study med start date, assign as concomitant
 
Cannot be assigned as 'post treatment'

	Partial	
Impute stop date as latest possible date (i.e. last day of month if day unknown or 31st December if day and month are unknown), then:
 
If stop date < study med start date, assign as prior
 
If stop date >= study med start date, assign as concomitant
 
Cannot be assigned as 'post treatment'

	Missing	Assign as concomitant

Document: \\needc-vnasc01\Biosdata\Menarini\NebAm\ZZA67778\Biostatistics\Documentation\SAP\SAP_Menarini_MEIN21AmNe-Hyp001_Final_V1.0

Author: [name]

Version Number:

Final V1.0

Version Date:

11Nov2022

Template No.: CS_TP_BS016 Revision 7

Reference: CS_WI_BS005

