## 8.2.1 Physical Examination

Physical examination will be performed according to the local practice. Physical examination will consist of the following body systems: eyes, ears, nose, throat, cardiovascular system, respiratory system, gastrointestinal system, dermatologic system, extremities, musculoskeletal system, nervous system, and lymph nodes. Height and weight will also be recorded at screening. Any new finding, or worsening of a previous finding, should be reported as a new AE.

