6. GENERAL CONSIDERATIONS

6.1. Reference Start Date and Study Day

Study Day will be calculated from the reference start date and will be used to show start/stop day of assessments and events. It will appear in every listing where an assessment date or event date appears.

Reference start date is defined as the day of the first dose of study (combination therapy) (Visit 2), (Day 1 is the day of the first dose of study drug).

- If the date of the event is on or after the reference date, then:
 - Study Day = (date of event – reference date) + 1.
- If the date of the event is prior to the reference date, then:
 - Study Day = (date of event – reference date).

In the situation where the event date is partial or missing, Study Day, and any corresponding durations will appear partial or missing in the listings.

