6.2. Baseline

Unless otherwise specified, baseline is defined as the last non-missing measurement taken same day or prior to reference start date (including unscheduled assessments) before first dose of study medication (i.e., combination therapy). Adverse Events (AEs) and medications commencing on

Document: \\weedc-vnasc01\Biosdata\Menarini\NebAm\ZZA67778\Biostatistics\Documentation\SAP\SAP_Menarini_MEIN21AmNe-Hyp001_Final_V1.0

Author: [name]

Version Number:

Final V1.0

Version Date:

11Nov2022

Template No.: CS_TP_BS016 Revision 7

Reference: CS_WI_BS005

Effective Date: 01Nov2021

the reference start date/time will be considered post-baseline, unless the start time of the AE is known to be prior to the first dosing of the study drug. Since there is no Lab assessment in Visit 2, Lab values collected at Visit 1 will be considered baseline for Lab data.

For combination therapy related analysis, the baseline will be the measurements that are taken at Visit 2 (Week 0). For safety analysis, if the measurement at visit 2 is missing or not collected, then visit 1 data will be considered.

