18.1. Adverse Events

Adverse Events (AEs) will be coded using Medical Dictionary for Regulatory Activities (MedDRA) central coding dictionary, Version 25.0 or latest.

Treatment emergent adverse events (TEAEs) are defined as new AEs that occur on or after the date/time of the first administration of study medication (i.e., monotherapy and/or combination therapy) or worsen if an AE started prior to the start of first administration of study medication.

TEAEs that occurred or worsened on or after the date/time of the first administration of Monotherapy but before the date/time of the first administration of Combination Therapy will be summarized under “Monotherapy”.

TEAEs that occurred or worsened on or after the date/time of the first administration of Combination Therapy will be summarized under “Combination Therapy”.

See Appendix 2 for handling of partial dates for AEs. In the case where it is not possible to define an AE as treatment emergent or not, the AE will be classified by the worst case, i.e., treatment emergent.

An overall summary of number of subjects within each of the categories described in the subsection below, will be provided as specified in the templates.

Listings will include TEAEs and Non-TEAEs.

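### SAP Appendix 2 has no branch for worsening and so contradicts the TEAE definition in SAP 18.1; its anchor date is undefined, and partial dates that straddle the phases get no phase

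*SAP*

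**What the plan says.** SAP 18.1 defines a treatment-emergent adverse event (TEAE) in two limbs: a new event on or after first dosing, or an earlier event that gets worse, "or worsen if an AE started prior to the start of first administration of study medication". Protocol 12.5.6 has the same two limbs. SAP 18.1 takes the starting point as the "first administration of study medication (i.e., monotherapy and/or combination therapy" and then splits TEAEs by phase according to when they began or worsened. Those from the first monotherapy dose "but before the date/time of the first administration of Combination Therapy will be summarized under “Monotherapy"; those from the first combination dose onward go under Combination Therapy.

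Appendix 2 holds the algorithm for treatment emergence. Its row for a known start date reads "If start date < study med start date, then not TEAE". Its next row, for a start date described as "Partial, but known components show that it cannot be on or after study med start date", also gives not treatment-emergent. Neither row mentions worsening, and no row mentions the first combination dose.

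Appendix 2 compares every date with a 'study med start date' that the SAP does not define. Elsewhere the SAP uses the underlying term in two ways. Section 6.2 sets baseline "before first dose of study medication (i.e., combination therapy", which means combination only. Sections 5.3 and 18.1 mean monotherapy and/or combination. Section 6.1 adds a separately named date: "Reference start date is defined as the day of the first dose of study (combination therapy) (Visit 2".

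**The concern.** The study adds a second drug at Visit 2 and may raise the amlodipine dose at Visit 3. The safety of the monotherapies and of the combinations is a secondary objective. An event that was present earlier and gets worse after a treatment step is therefore one the safety tables should show, and SAP 18.1 says they will. If the program follows Appendix 2 instead, an event that began before the anchor date is dropped from the TEAE tables however much it worsens later.

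Two further gaps bear on the same tables. Because the anchor is undefined, two programmers could choose different dates. And an event whose start date is partial or missing can be accepted as treatment-emergent with nothing to say which phase column it belongs in.

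**Working it through.** There is no stated figure to reproduce. The check applies both rules to the same events.

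**1. Emergence with known dates.** Put the first monotherapy dose at day 0 and the first combination dose at day 28. Apply SAP 18.1, then Appendix 2 with each possible anchor.

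| Event | SAP 18.1 | Appendix 2, anchor day 0 | Appendix 2, anchor day 28 |
|---|---|---|---|
| Starts day −3, does not worsen | not TEAE | not TEAE | not TEAE |
| Starts day −3, worsens day 10 | TEAE, Monotherapy | not TEAE | not TEAE |
| Starts day −3, worsens day 35 | TEAE, Combination | not TEAE | not TEAE |
| Starts day 10, does not worsen | TEAE, Monotherapy | TEAE | not TEAE |
| Starts day 10, worsens day 35 | TEAE, Monotherapy, and Combination on worsening | TEAE | not TEAE |
| Starts day 35 | TEAE, Combination | TEAE | TEAE |

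With the monotherapy anchor, Appendix 2 disagrees with SAP 18.1 on 2 of the 6 patterns; with the combination anchor, on 4 of 6. The two patterns that start before day 0 and then worsen conflict under either anchor, so the contradiction on worsening does not depend on how the anchor is read.

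**2. Which anchor is meant.** SAP 6.1 and 6.2 point towards the combination. Section 6.2 also treats events that begin on the first combination day as post-baseline. Three things point the other way:
- Appendix 2 uses the same undefined term in its medication algorithm, where a drug stopped before that date is prior. SAP 13 defines prior medication by the first dose of monotherapy. Within the appendix, the term therefore matches the first monotherapy dose.
- SAP 18.1, which governs adverse events, reads study medication as either therapy.
- SAP 18.1 provides a Monotherapy category, which would serve little purpose if known-date run-in events could not be treatment-emergent.

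The reference start date in SAP 6.1 is a different term, and Appendix 2 does not use it.

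**3. Phase with incomplete dates.** Take a partial start that could be any day from 5 to 34.
- Stop on day 40: TEAE under both anchors. The start may lie on either side of day 28, and neither SAP 18.1 nor Appendix 2 assigns a phase.
- Stop on day 20: TEAE under the monotherapy anchor, not under the combination anchor. Here the stop date places the event in run-in.
- Start and stop both missing: Appendix 2 assumes TEAE. Again no phase is given.

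**4. How many events can be affected under the monotherapy anchor.** Protocol 9.9 collects events after consent, and protocol 5 starts the run-in on the day of screening. The time for an event to start before the first monotherapy dose is therefore short. Appendix 2 compares whole dates, so an event starting on the day of that dose is already treatment-emergent. What remains is an event whose recorded onset falls on an earlier day, such as a pre-existing condition that worsens and is entered with its original onset. The documents give no count of such records. SAP 18.1 lists non-TEAEs as well as TEAEs, so these events remain in the listings.

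**The case against.** The best defence is one of hierarchy. Appendix 2 is titled as a set of partial-date conventions, and SAP 18.1 cites it only for partial dates. SAP 18.1 would then govern known dates, with its worsening limb and phase rule intact. This has weight, but the appendix's first row states a result for fully known start dates, under a heading that presents it as the emergence algorithm. The clearly-earlier partial row lies within the appendix's remit on any view, and it too omits worsening.

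The second defence is that worsening produces a new record with its own start date. Protocol 8.2.1 says "Any new finding, or worsening of a previous finding, should be reported as a new AE", and protocol 9.9 requires clinically relevant worsening of laboratory abnormalities to be reported as an adverse event. Those rules cover examination and laboratory findings. No equivalent is stated for other events, such as symptoms. The eCRF guidelines are not among the documents and may cover it.

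Three stronger readings are tempting but not supported:
- A reader might infer that every run-in event drops out and the Monotherapy column is empty. That needs the combination anchor, which SAP 13 and 18.1 make unlikely.
- A reader might try to count run-in events that worsen on the combination. Assuming that 10–20% of about 220 patients have a run-in event and that 10–20% of those worsen gives 220 × 0.10 × 0.10 = 2.2 to 220 × 0.20 × 0.20 = 8.8. The rates are not in the documents. Under the monotherapy anchor these events are already TEAEs in Appendix 2, and SAP 18.1 phases them by when they worsened.
- A reader might say that Appendix 2 contradicts SAP 18.1 on phase. It is silent on phase, and for fully dated events SAP 18.1 supplies the answer.

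**Conclusion.** The contradiction on worsening is real under either anchor. Appendix 2 excludes events that SAP 18.1 and protocol 12.5.6 include. The anchor lacks a definition, although the SAP read as a whole points to the first monotherapy dose. Partial or missing starts that could fall on either side of the first combination dose have no phase rule; the SAP's worst-case default settles emergence only.

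The likely effect is small. It rests on the monotherapy anchor, collection of events from consent and a same-day start of run-in. Affected events would be missing from the TEAE summaries but present in the listings. No numerical size can be derived from the documents. The point is still worth correcting, because a stated rule is wrong as written and the correction is cheap.

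**What to change.** Make three edits to Appendix 2:
1. Define study med start date as the date of the first monotherapy dose.
2. In the known-date row and the clearly-earlier partial row, add that an event with an earlier start that worsens on or after that date is a TEAE.
3. Add a step that applies the phase rule in SAP 18.1, by onset or worsening, against the first combination dose date. State a default for partial or missing starts that could lie on either side. The present worst-case rule does not supply this default, so it has to be chosen and written down.

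Before database lock, confirm that the adverse event data identify the date of worsening for events ongoing at Visit 2. Where they do not, query those events at the data review that SAP 9.2 already plans.

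A new requirement to enter every worsening as a separate record is not proposed. It would change data collection late: the SAP is dated 11 November 2022, and the protocol planned last patient out for early December 2022.

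The cost is a few lines of SAP text, minor programming, and queries limited to events ongoing at Visit 2 that lack a worsening date.
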